Protocol

The effects of a fasted versus fed remote walking-based training programme on glycaemic control in overweight individuals

Short title: Can fasted exercise enhance glycaemic control in overweight individuals?

Investigators:

[name]

PhD Student, School of Sport and Exercise Sciences, Liverpool John Moores University

[name]

Lecturer in Exercise and Health Metabolism, School of Sport and Exercise Sciences, Liverpool John Moores University

[name]

Reader and Honorary Consultant Physician, University of Liverpool and Aintree University Hospital

[name]

Professor of Exercise Metabolism, School of Sport and Exercise Sciences, Liverpool John Moores University

[name]

Lecturer in Sport and Exercise Nutrition, School of Sport and Exercise Sciences, Liverpool John Moores University

Background and rational:

According to recent statistics, 64.3% of the UK adult population are now classified as overweight or obese. People who are overweight or obese have high levels of fat in their muscle, which is linked to insulin resistance and ultimately the development of type 2 diabetes. Interestingly, healthy people also have high levels of muscle fat, but they are highly insulin sensitive. This is because healthy people are able to burn this fat to generate energy during exercise, resulting in a reduction in the amount of fat in the muscle that can then be replaced with a meal. Healthy people who regularly breakdown these stores during exercise, and rebuild them following exercise, have a high turnover of their fat stores. However, people who are overweight or obese have difficulty using muscle fat during exercise. Fasted exercise has been shown to increase the reliance on muscle fat stores during exercise and is well utilised in trained individuals to improve their capacity to burn fat. Whether this type of exercise has the potential to be beneficial in less healthy individuals is less well known. Most importantly, whether this simple exercise-nutrition strategy can be implemented into the daily lives of less healthy individuals to improve glycaemic control and reduce type 2 diabetes risk now requires investigation.

Aim: To determine whether a remote 12-week fasted walking-based intervention can increase glycaemic control compared to a fed group.

Participants: N = 34

Inclusion criteria

You are likely to be eligible for this study if you fulfil the following criteria:

[figure not shown]
- Aged 20-60 years
- BMI $>28 \text{ kg.m}^{-2}$
- Not currently using any anti-diabetes medication
- Physically inactive (performing less than two 30 min structured exercise sessions per week for the last year)
- Not pregnant or currently breast feeding
- Pre-menopausal or peri-menopausal
- Not currently involved in a weight loss programme or using weight loss medication

Exclusion Criteria

(Meeting any of the following criteria will prevent you from participating in the study)

- Involved in regular exercise (engaged in more than 3 sessions of structured exercise of $>30 \text{ min}$ per week)
- Currently using anti-diabetes medication (e.g. insulin, metformin)
- Pregnant or breast feeding
- Currently engaged in active weight loss programme or using weight loss medication
- Diagnosed with chronic kidney disease
- Post-menopausal

Plan of investigation

Consent and pre-screening:

Participants will be sent a participant information sheet after expressing interest via email and will have the opportunity to contact with any questions about the study before providing consent via email.

Questionnaire: Participants will complete a Readiness to Exercise questionnaire and send via email to ensure they are fit to undertake exercise as part of the study.

Pre-testing:

Waist-to-hip ratio and weight: Participants will be provided with a tape measure and instructions on how to measure waist circumference and hip circumference. From this, waist-to-hip ratio will be calculated. Additionally, participants will be asked to use their own scales to provide their weight (if they don't have any they will be provided).

Blood pressure: (pending [name] suggestion for this)

Baseline blood sample: Participants will receive blood sample kits containing (Thriva) full instructions that will be used to measure fasting insulin, glucose, lipid profile, HbA1c, cholesterol (includes triglycerides), liver enzymes (ALT usually elevated in people with NAFLD). A researcher will be available to video call if needed while these are being completed.

CGM: Participants will receive a continuous blood glucose monitor that contains full instructions to fit and use. These will be worn for two weeks – 1 week before the intervention and during the first week of the intervention (see Fig. 1).

Diet: Participants will receive a food diary to record their habitual dietary intake for three days (24 hours after the CGM is fitted). During the first week on the intervention they will also be asked to write down what they eat for lunch on the days they exercise.

Fitness test: Participants will receive a polar beat heart rate monitor and instructions on how to download an app containing a bleep test protocol. They will be asked to complete the bleep test wearing the HR monitor **at least 48 hours before they begin the intervention.**

Exercise intervention:

Pairs of participants from each group (matched for gender, age, BMI and) will be randomized to undertake 12 weeks of steady walking in either a fasted state (before breakfast each day) or a fed state (after breakfast each day). They will be asked to eat the same breakfast on each day they complete the exercise, whether it is before or after.

Walking sessions will be 4 times per week and will be two continuous sessions (~50% HR max) and two interval sessions (3 minutes at 40% HR max, 3 minutes 80% HR max) monitored by the polar beat app. Participants will initially walk for 30 minute sessions in week 1 and this will increase by 5 minutes each week until they are completing 4x 60 minute sessions per week (see table.1).

A CGM will be in place during week 1 to measure the glycaemic response to exercise. And a second CGM will be inserted at the beginning of week 12 to see the changes in glycaemic control on exercise days and will remain in place for post-intervention CGM monitoring.

Post-testing:

The post intervention assessments will be identical in all aspects to the pre-intervention assessments and will begin ≥ 72 hours after the final training session.

Proposed analysis:

Adherence: From the training data, we will monitor adherence to the study intervention since this is remotely ran. We will also monitor whether participants hit their target HR zones during each exercise bout.

Blood samples: All blood samples will be analysed by Thriva.

CGM: The 24 h glycaemic profile obtained during the CGM period will be used to determine average glucose levels, and the prevalence of hyperglycaemia and hypoglycaemia. Based on the ADA/EASD guidelines, the prevalence of hyperglycaemia and hypoglycaemia will be defined as the total time during which glucose concentrations are >10 mmol.L $^{-1}$ or <3.9 mmol.L $^{-1}$, respectively. The primary outcome from the CGM data will be the time spent in range (3.9 – 10 mmol.L $^{-1}$).

CGM data collection
Pre-testing week
Intervention Week 1
CGM

Day 1	Day 2	Day 3	Day 4	Day 5	Day 6	Day 7	Day 8	Day 9	Day 10	Day 11	Day 12	Day 13	Day 14	Intervention weeks 2-11
Fasting blood samples	Normal diet recorded	Normal diet recorded					Walking session Lunch recorded		Walking session Lunch recorded		Walking session Lunch recorded	Walking session Lunch recorded		

Intervention Week 12
Post-testing week
CGM

Intervention weeks 2-11	Day 1 Walking session Lunch recorded	Day 2	Day 3 Walking session Lunch recorded	Day 4	Day 5 Walking session Lunch recorded	Day 6 Walking session Lunch recorded	Day 7	Day 8 Fasting blood samples	Day 9 Normal diet recorded	Day 10 Normal diet recorded	Day 11	Day 12	Day 13	Day 14
-------------------------	--------------------------------------	-------	--------------------------------------	-------	--------------------------------------	--------------------------------------	-------	-----------------------------	----------------------------	-----------------------------	--------	--------	--------	--------

Figure 1. Plan of CGM data collection. Participants will wear a CGM at two time points; once at the beginning of the study and once at the end. Each CGM time point will measure one resting week and one intervention week.

Table 1. An outline of the walking-based exercise programme. All participants will follow the same intervention make up of 4 sessions per week; 2 continuous walking sessions and 2 interval walking sessions.

Week 1 & 2		Week 7 & 8:	
Session 1: continuous	30 min	Session 1: continuous	45 min
Session 2: Interval	30 min	Session 2: Interval	48 min
Session 3: continuous	30 min	Session 3: continuous	45 min
Session 4: Interval	30 min	Session 4: Interval	48 min
Week 3 & 4:		Week 9 & 10	
Session 1: continuous	35 min	Session 1: continuous	50 min
Session 2: Interval	36 min	Session 2: Interval	54 min
Session 3: continuous	35 min	Session 3: continuous	50 min
Session 4: Interval	36 min	Session 4: Interval	54 min
Week 5 & 6:		Week 11 & 12	
Session 1: continuous	40 min	Session 1: continuous	60 min
Session 2: Interval	42 min	Session 2: Interval	60 min
Session 3: continuous	40 min	Session 3: continuous	60 min
Session 4: Interval	42 min	Session 4: Interval	60 min

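### Does the mismatch between a three-day diet diary in the text and two days in Figure 1 make diet before and after the intervention non-comparable?

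*Protocol*

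**What the plan says.** Under Pre-testing: Diet, participants are to "record their habitual dietary intake for three days (24 hours after the CGM is fitted". The first sensor is worn "1 week before the intervention and during the first week of the intervention (see Fig. 1", so that instruction leads into the resting week.

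Figure 1 marks diary days with "Normal diet recorded". In the pre-testing week these are Days 2 and 3, and Days 4 to 7 are empty. In the second sensor period the entries are "Day 9 Normal diet recorded" and "Day 10 Normal diet recorded", and Day 11 is empty.

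Under Exercise intervention, "a second CGM will be inserted at the beginning of week 12". That is a training week.

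Under Post-testing, one sentence makes two statements: "The post intervention assessments will be identical in all aspects to the pre-intervention assessments", and they "will begin ≥ 72 hours after the final training session".

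**The concern.** Two things look wrong at first.

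- **Length.** The text says three days and the figure says two, at both time points. In the follow-up row every cell carries its own day label. In the baseline row the blanks for Days 4 to 7 line up with the walking session on Day 8. A broken table is therefore an unlikely explanation, and the contradiction is real.
- **Timing at follow-up.** The only start rule the text gives for the diary is sensor fitting. If post-testing copies pre-testing in every respect, that rule would put the follow-up diary in the first days of week 12, while participants are still walking.

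The arms differ in whether breakfast comes before or after exercise, so intake is an obvious competing explanation for a glycaemic difference. If the baseline diary covered rest days and the follow-up diary covered training days, an arm-specific change in eating on training days could pass for a change in habitual diet. If some participants kept two days and others three, precision would also vary between them.

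**Working it through.** **Inputs.** Diary length and start come from Pre-testing: Diet, sensor timing from Pre-testing: CGM and Exercise intervention, the 72-hour rule from Post-testing, and the calendar from Figure 1. Fitting on Day 1 of each 14-day period is an assumption, because the sensor bar in the figure is not readable. It agrees with the text for both sensors.

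**Step 1: the possible windows.**

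| Rule | Baseline | Follow-up |
|---|---|---|
| Sensor fitting + 24 h, three days | Days 2–4, no walking | Days 2–4 of week 12, walking on Day 3 |
| Figure 1, two days | Days 2–3, no walking | Days 9–10, no walking |
| Figure 1 start, three days | Days 2–4, no walking | Days 9–11, no walking |

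Only the first row gives unlike periods.

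**Step 2: is the first row permitted at follow-up?** Figure 1 has the last walking session on Day 6 of the second period. A diary on Days 2–4 comes before that session, whereas Post-testing requires assessments to start at least 72 hours after it. The text therefore excludes the first row without help from the figure.

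**Step 3: does Figure 1 satisfy the 72-hour rule for the diary?** Day 9 − Day 6 = 3 calendar days = 72 hours, reached on Day 9 at the clock time when the Day 6 walk ended. The diary meets the rule to within part of a day. The blood sample on Day 8 falls about 48 hours after the Day 6 walk, but that is a separate matter from diet.

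**Step 4: are the Figure 1 windows matched?** Day 9 is the second day of the post-testing week (9 − 7 = 2) and Day 10 is the third (10 − 7 = 3). Baseline uses Days 2 and 3. Position in the week, number of days, absence of walking and place directly after the fasting sample (Day 1 and Day 8) all agree.

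**Step 5: what does the length cost?** With independent days and day-to-day variance σ², a person's mean over k days has day-to-day variance σ²/k.

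- Variance ratio, two days to three: (σ²/2) / (σ²/3) = 3/2 = 1.5.
- Standard error ratio: √1.5 = 1.22, an increase of 22%.

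This is an upper bound for a comparison of arms. Total variance also holds a component τ² for true differences between people (or, for change scores, differences in true change). Diary length does not affect τ², so for a follow-up mean the ratio is (τ² + σ²/2) / (τ² + σ²/3), which is below 1.5 whenever τ² > 0. The same holds for change scores, with 2σ² in place of σ².

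**The case for a change.** The strongest opposing case is that the text and the figure disagree on length, so the figure cannot simply be taken as governing. In addition, the text's only start rule for the diary cannot be met at follow-up together with the 72-hour rule: if post-testing is identical in every respect, one of the two must give way. The study is remote and participants fit their own sensors from instructions, so someone could start the second diary the day after fitting. Putting this right would take one sentence and one figure.

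Part of this stands. The length contradiction is genuine, and the text does not restate a start point for the follow-up diary. The step from there to a biased comparison does not stand. The sensor-fitting rule sits under Pre-testing, where fitting and the resting week coincide. The second sensor is fitted early for a stated purpose, to capture glucose on exercise days, and intake in that week is covered separately by lunch recording. The Post-testing section and Figure 1 together leave one sensible place for the follow-up diary, and that place matches baseline. For bias to arise, a participant or the study team would have to disregard both the 72-hour rule and the figure.

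**Conclusion.** The concern does not call for a change to the plan. The three-versus-two mismatch is a clerical slip, and the follow-up start point is a small gap in the text that Figure 1 fills. The claim that diet before and after is not like for like fails, because the protocol's own 72-hour rule excludes the week-12 reading and the scheduled windows agree in position and length.

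The size is at most a 22% larger day-to-day standard error for a person's mean intake, and less for a comparison between arms. Diet is a supporting measure. The Proposed analysis section covers adherence, blood samples and CGM data and states no use of the diary, and the primary CGM outcome, time in range, does not draw on it. Either length, applied alike to both arms and both time points, leaves the glycaemic conclusion as sound as before.

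This rests on three assumptions: sensors are fitted on Day 1 of each period, the follow-up diary is kept in the post-testing week as Figure 1 shows, and one length is used throughout. A statistical analysis plan, not at hand, might use the diary data. If it did, the matched windows would still hold and the bound above would still apply.

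### The same-breakfast rule fixes breakfast within a participant but not independently of arm, and breakfast goes unrecorded on walking days, so the week 1 response and any absolute week 12 exercise-day contrast could mix meal timing with meal content

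*Protocol*

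**What the plan says.** Under Exercise intervention, the Protocol describes a parallel-group design: "Pairs of participants from each group (matched for gender, age, BMI and) will be randomized to undertake 12 weeks of steady walking", with one arm walking before breakfast and the other after it. The only control on the meal is: "They will be asked to eat the same breakfast on each day they complete the exercise, whether it is before or after". No content, energy or carbohydrate level is set, no meal is supplied, and diet is not among the readable matching factors.

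The dietary records are described under Pre-testing (Diet). Before the intervention, "Participants will receive a food diary to record their habitual dietary intake for three days". On walking days the record is narrower: "During the first week on the intervention they will also be asked to write down what they eat for lunch on the days they exercise". Figure 1 also shows lunch as the only meal recorded on the walking days of week 12.

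The CGM is worn through the walking days of weeks 1 and 12. The first week is there to capture the glucose response to walking, the second to show how exercise-day control has changed. Under Proposed analysis (CGM), "The 24 h glycaemic profile obtained during the CGM period will be used to determine average glucose levels", and time between 3.9 and 10 mmol/L is the primary CGM outcome. The Adherence paragraph covers training data and heart-rate zones; it does not mention breakfast.

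**The concern.** The question is whether the timing of walking relative to breakfast matters, so breakfast is the meal whose content most needs to be comparable between arms. Participants cannot be blind to whether they eat before or after walking, and nothing requires the meal to be named before they learn their arm. A participant may choose one kind of breakfast when a walk follows and another when the walk is already done.

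Breakfast glucose falls within the 24-hour profile on every walking day. If the choice depends on arm, a difference between arms in walking-day glucose could reflect what was eaten as well as when. Repeating the same meal would not average this out over the days of one week. As breakfast is not written down on those days, the difference could be neither seen nor adjusted for, and nobody could confirm that the instruction had been followed. An analysis plan cannot repair this later, because the data would not exist.

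**Working it through.** **1. What the rule protects.** Let *b* be the contribution of a participant's chosen breakfast to that participant's walking-day mean glucose, and Δb the difference in mean *b* between arms. Let τ1 and τ12 be the true arm differences in weeks 1 and 12.

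- Week 1 contrast: τ1 + Δb
- Week 12 contrast: τ12 + Δb
- Contrast of the changes: (τ12 + Δb) − (τ1 + Δb) = τ12 − τ1

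If each person keeps one breakfast and its effect is additive, Δb cancels from the change and stays in both absolute contrasts. The cancellation is not perfect: if training lowers the response to a meal by a proportion *p* in both arms, a residue of −p × Δb remains. Hence largely protected, not fully. Nor does the change measure an effect already present in week 1, since both CGM walking weeks come after allocation and there is no walking-day baseline.

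**2. Where Δb can come from.** It has two parts: choice that depends on arm, and chance. Randomisation makes the habitual breakfast equal on average, so bias needs the first part.

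The chance part can be sized in SD units. The Protocol gives N = 34; I assume 17 per arm and ignore any gain from pairing.

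- SE of an arm difference = √(2/17) = 0.343 SD
- 95% range = ±1.96 × 0.343 = ±0.67 SD

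So the arms' mean breakfast carbohydrate, for example, could differ by up to about 0.67 SD by chance alone.

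**3. Possible size on a walking day.** The Protocol gives no figure. Assume that different breakfasts shift glucose by 0.5 to 1.0 mmol/L over the 3 hours after the meal.

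- Walking-day 24-hour mean: 3/24 × 0.5 = 0.0625, and 3/24 × 1.0 = 0.125 mmol/L
- Mean over a walking week with 4 walking days in 7: 0.0625 × 4/7 = 0.036, and 0.125 × 4/7 = 0.071 mmol/L

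By Figure 1 the CGM covers 4 + 4 = 8 walking sessions. These are shifts in mean glucose. Time in range changes only if a shift carries readings across 3.9 or 10 mmol/L, and the Protocol gives nothing from which to estimate that.

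**4. Possible effect on an absolute test.** Suppose that meal timing has no true effect, that arm-dependent breakfasts shift exercise-day glucose by *s* (in SD of that outcome), and that the test is two-sided at 5%. The rejection probability is Φ(s/0.343 − 1.96) + Φ(−s/0.343 − 1.96).

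| Assumed shift *s* | Rejection probability |
|---|---|
| 0 | 5% |
| 0.2 SD | 9% |
| 0.3 SD | 14% |
| 0.5 SD | 31% |

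The values of *s* are assumptions. The table shows sensitivity and is not an estimate for this trial.

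**5. No planned figure to reproduce.** N = 34 is stated without alpha, power, effect size or SD, so it cannot be recomputed. The point does not depend on it.

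**The case against.** The strongest reply is that the rule does the job the Protocol gives the second CGM. That device is there to show change on exercise days, and a breakfast held constant within a person largely drops out of change. This stands, provided the instruction is followed. It leaves exposed the week 1 response, which the Protocol also names as a purpose of the CGM, and any absolute contrast in week 12, which the Protocol neither plans nor excludes.

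Much of the outcome set also lies outside the rule. Each CGM period includes a resting week, and fasting glucose, insulin and HbA1c are measured before and after. This stands as well: walking-day breakfast does not act directly on them.

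A third reply is that in a free-living trial a change of breakfast brought about by allocation is part of the strategy's effect. That is a legitimate choice of estimand, and the Protocol does not settle it. Asking for a constant breakfast suggests that the meal is meant to be held fixed. On either view, breakfast has to be recorded before anyone can say what the contrast contains.

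A reader might go further and infer that the sentence claims to match breakfast between arms. It need not: it can equally mean that the consistency rule applies in both arms. A reader might also infer that fasted walkers would eat more afterwards, which would hide a benefit. Nothing in the Protocol supports a direction. It also does not say when participants settle on a breakfast or when allocation is disclosed; the point is only that it leaves room for choice after disclosure.

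**Conclusion.** The concern holds in a limited form. The rule largely protects the week 1 to week 12 change in exercise-day glucose if it is followed. It does not prevent breakfast content from depending on arm, and with only lunch recorded on walking days, neither that dependence nor compliance can be checked. The week 1 glucose response and any absolute week 12 exercise-day comparison could mix timing with content.

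The direction and size are unknown. The shift of about 0.06 to 0.13 mmol/L in the walking-day mean rests wholly on the assumed 0.5 to 1.0 mmol/L over 3 hours, and no effect on time in range has been shown. The documents do not support reading this as a flaw in the glycaemic comparison as a whole. It is a gap in one part of it that costs little to close.

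**What to change.** - Have each participant name the exercise-day breakfast from their own pre-testing food diary before allocation is disclosed, and keep it in whichever arm they enter.
- Add breakfast to the lunch record on walking days in both CGM weeks.
- Report the energy and carbohydrate of that breakfast by arm.
- State that change from week 1 to week 12 is the main exercise-day comparison, and label the week 1 response and any absolute week 12 contrast as more exposed to breakfast content.

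This removes arm-dependent choice as far as participants comply, and makes compliance checkable. It does not remove chance imbalance at N = 34, but the record would show how large that is.

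The cost is a sentence or two in the Protocol and participant instructions and a little extra diary coding, with no added visit or device. Participants lose some freedom to change breakfast once they know their arm.

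### The low interval phase is prescribed at 40% HR max, close to an assumed resting heart rate, and most inactive participants could not hold it while walking

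*Protocol*

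**What the plan says.** Under 'Exercise intervention', half of each week's walks are described as "two interval sessions (3 minutes at 40% HR max, 3 minutes 80% HR max) monitored by the polar beat app". The other half are steady walks with a target of about 50% of HR max. The legend of Table 1 applies this to everyone: "All participants will follow the same intervention make up of 4 sessions per week; 2 continuous walking sessions and 2 interval walking sessions". All sessions are walking.

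Under 'Proposed analysis', the Adherence paragraph gives the remote setting as the reason for tracking adherence ("From the training data, we will monitor adherence to the study intervention since this is remotely ran") and adds: "We will also monitor whether participants hit their target HR zones during each exercise bout". No zone width is given. The text does not say whether a target is a floor or a band, or whether each 3-minute phase is scored.

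The inclusion criteria give "Aged 20-60 years" and "Physically inactive (performing less than two 30 min structured exercise sessions per week for the last year". Under 'Fitness test', participants wear a heart-rate monitor for a remote bleep test. The protocol does not say whether HR max is taken from that test or from an age formula, and it does not mention heart rate reserve.

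**The concern.** A percentage of HR max starts from zero, not from the resting rate, so a low percentage can fall at or below rest. If 40% does so here, a participant who follows the instruction literally must slow nearly to a stop in the low phases. One who keeps walking misses the stated target.

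Two things are at stake. The first is a prescription that cannot be followed for part of every interval session, in a programme run without supervision. The second is the adherence record: if the low phases are scored against the target, the result may say more about the scoring rule than about whether the session was walked as planned.

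**Working it through.** The protocol gives no bpm values, so there is no figure of its own to reproduce.

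**Inputs from the protocol:** ages 20 to 60; intensities of 40%, about 50% and 80% of HR max; 3-minute phases; the session lengths in Table 1.

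**Assumptions:** HR max = 220 − age, or 208 − 0.7 × age; resting rate 60 to 80 bpm; easy walking adds 10, 20 or 30 bpm to rest.

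**1. Targets in bpm (220 − age)**

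| Age | HR max | 40% | 50% | 80% | Fall from 80% to 40% |
|---|---|---|---|---|---|
| 20 | 200 | 80 | 100 | 160 | 80 |
| 40 | 180 | 72 | 90 | 144 | 72 |
| 60 | 160 | 64 | 80 | 128 | 64 |

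With 208 − 0.7 × age, HR max is 194, 180 and 166, and 40% is 77.6, 72 and 66.4 bpm. If HR max comes from the bleep test and differs by 10 bpm, the target moves by 0.40 × 10 = 4 bpm, so the overall range is 60 to 84 bpm.

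**2. Room above rest (40% target minus rest, 220 − age, ages 20/40/60)**

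- Rest 60: 20, 12, 4 bpm
- Rest 70: 10, 2, −6 bpm
- Rest 80: 0, −8, −16 bpm

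As a share of heart rate reserve at age 40 and rest 70: (72 − 70)/(180 − 70) = 1.8%.

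On an even grid of 41 ages by 21 resting rates, the target is at or below rest in 41% of combinations with either formula. With walking at rest + 10, + 20 or + 30 bpm, heart rate is at or below the target in 17%, under 1% and 0% (second formula: 14%, 0%, 0%).

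**3. How much of the programme**

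- Interval minutes: (30 + 36 + 42 + 48 + 54 + 60) × 4 = 1080. Half of this is low phase: 540 minutes = 180 phases of 3 minutes.
- Continuous minutes: (30 + 35 + 40 + 45 + 50 + 60) × 4 = 1040. Total: 2120.
- Share: 540/2120 = 25.5%.
- With the low phase first in each of the 24 interval sessions, 180 − 24 = 156 low phases follow an 80% bout: 468 minutes, 468/2120 = 22.1%.
- Each of these needs the fall in step 1 within 3 minutes. A ±10 bpm tolerance on both phases takes off 20 bpm and leaves 60, 52 and 44 bpm.

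**4. What scoring the low phase would show** (same grid, no carry-over from the 80% bout; share of combinations meeting the rule)

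| Rule | Formula | +10 | +20 | +30 |
|---|---|---|---|---|
| At or below 40% + 10 bpm | 220 − age | 60% | 17% | <1% |
| | 208 − 0.7 × age | 60% | 14% | 0% |
| At or below 50% HR max | 220 − age | 87% | 51% | 14% |
| | 208 − 0.7 × age | 90% | 50% | 10% |
| At least 40% | 220 − age | 84% | 100% | 100% |
| | 208 − 0.7 × age | 86% | 100% | 100% |

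Carry-over would lower the shares under the two ceiling rules and raise those under the floor rule.

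**The case against.** The order 40%, about 50%, 80% is coherent: the easy part of an interval session is expected to lie below a steady walk. A reader might infer that a low phase below the continuous-walk target contradicts the protocol. It does not, and the point does not rest on it.

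The bpm values, resting rates and walking increments are all assumed, and the inclusion criteria limit structured exercise without giving any heart rate. This is fair. The result for the prescription is nevertheless stable across both HR max formulas and a 10 bpm error in HR max. Some participants could comply: at age 20 and rest 60 there are 20 bpm of room, or 30 with a ±10 bpm zone.

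A reader might also infer that low-phase adherence is uninformative however it is scored. The documents do not support that. The result depends on zone width: with a ceiling at 50% HR max, about half of the combinations comply at + 20 bpm before carry-over. Nor does the text say that each low phase is scored on its own; a bout may mean a whole session. Width and scoring rule may properly be left to the analysis plan. The prescribed intensity may not, because it stands in the protocol and is what participants are told to do.

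Finally, little depends on it. Adherence is only monitored; no threshold, exclusion or analysis set is tied to it.

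**Conclusion.** The point holds as a minor one. At 64 to 80 bpm (66 to 78 with the second formula), the low-phase target lies within the assumed resting range, and most low phases begin straight after an 80% bout. For most inactive participants it cannot be held while walking, though not for all.

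If the low phases are scored, a narrow zone such as ±10 bpm would mostly be missed once walking adds 20 bpm or more, and an 'at least' rule would nearly always be met. A wider zone gives a mixed result.

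The effect is confined to the intensity prescription and the adherence report for 540 of 2120 minutes. The prescription is the same in both arms, so there is no ground for inferring a bias in the fasted-versus-fed comparison or in CGM time in range. The other 1580 minutes are unaffected. Confidence is medium, because the bpm figures rest on assumed HR max, resting and walking rates.

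**What to change.** Before the first participant starts, replace the 40% target in the interval prescription with three minutes of easy recovery walking, with heart rate still recorded but no target. Add one sentence under 'Adherence': *Interval sessions are scored on the 80% HR max phases and on session duration; the low-intensity phase is not scored.*

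If heart rate reserve was the intended base, restate all three intensities (40%, about 50%, 80%) on that base instead.

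The cost is one phrase and one sentence, with no new equipment or visits. The downside is that the low phase then has no heart-rate control, and zone adherence rests on 2120 − 540 = 1580 minutes (75% of those prescribed).
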